	UACR (x3)		x	x	x	x	DS	DS	DS
	Biomarkers		x	x		DS	DS		
Group	Immediate Start		x	x	x				
	Delayed Start		x	x	x	x	x	x	x

*CBC, Renal Panel, Ferritin, TSAT

** V1 if consent: CBC & eGFR panel

DS = Delayed Start ONLY

This is a two-arm, open-label, single-center, randomized controlled trial to understand the mechanisms of EIH. Participants will be randomized based on stratum of baseline level of urine albumin/urine creatinine ratios (UACR) measured on three consecutive days. The primary analysis will compare the 80 participants in the early start group to the 80 in the delayed start (DS) or waitlisted group over the first 12 weeks. All procedures will be performed as listed in the table based on study visit. Confirmatory analysis will compare the first 12 weeks to the next 12 weeks in the DS group. Accordingly, the study procedures labeled DS will be performed only in the delayed start randomized participants.

Study Intervention

Participants with CKD and anemia who meet the inclusion and exclusion criteria will be randomized to either the immediate or delayed start group. There are at least 7 study related visits in the early start group, and 11 in the waitlist group. Two consecutive days are needed to perform 24h ambulatory BP monitoring, which will be done twice in the immediate start group and 3 times in the delayed start group. Patients will receive oral iron (ferrous sulfate, 324 mg orally twice daily) if serum ferritin concentration is <100 ng/mL or transferrin saturation is <20%. If clinic BP exceeds either 179 mmHg systolic or 109 mmHg diastolic or if clinic BP raises by >20/10 mmHg compared to baseline, antihypertensive medication dose will be increased or a new antihypertensive will be added.

Participants will be identified in the renal clinic or the electronic medical record system based on estimated GFR and Hgb. At baseline, all participants will have 24-h urine Na measured to assess dietary Na intake.

Treatment Adherence

We recognize the limitations of syringe count, but we will assess treatment compliance with the study drug by performing a syringe count at each of the study visits.

Protocol for the management of anemia

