2. Change from baseline to 12 weeks in systolic BP in the comparisons above. Between group change in hypertension status from baseline to 12 weeks. Worsening of hypertension at any time point will be defined either as an increase in BP medication or an increase in seated clinic diastolic BP of ≥ 10 mmHg or systolic BP ≥ 20 mmHg. Within-group change in hypertension status from 12w to 24 w will be compared to the control period of 0 to 12w in the delayed start group.
3. The primary outcome variable in this aim is to examine the change in FMD from baseline to 4 weeks in those treated with EPO compared to the waitlisted group. The hypothesis being tested is that EPO will cause impairment in endothelial function. Accordingly, those on EPO will have worsening of FMD.
4. The primary outcome variable in this aim is to examine the predictors of change in FMD from baseline to 4 w in those treated with EPO compared to time controls. Predictors of this change will be baseline values of the following variables: ADMA, urine nitrate and nitrite, renin, aldosterone, and plasma endothelin-1 and change from baseline to 4 w in the above variables. This analysis will answer the question: which of the pathways independently is predictive of endothelial dysfunction?

Sample Size

The primary objective of the study is to assess the change from baseline to 12 weeks in diastolic BP in EPO treated patients compared to controls. In the waitlisted group, we will measure the change from 12 weeks to 24 weeks compared to the change from 0 to 12 weeks. We have measured 24h

ambulatory BP in 183 CKD patients 4 weeks apart. The mean diastolic BP at baseline was 68.3 mmHg and at 4 weeks 68.1 mmHg. The mean difference was 0.14 mmHg and the standard deviation of the difference was 10.3 mmHg. With these assumptions, two-tailed tests and 80% power, the required sample size to detect a between-group difference of 5 mmHg is 68 subjects completing the study in each group. Assuming 85% of those randomized complete the trial, we would need to randomize $68/0.85 = 80$ subjects per group, or 160 subjects in total.

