The standard deviation of the difference in systolic BP is 16.7 mmHg and we can detect an 8.4 mmHg between-group difference using the above assumption. The assessment of endothelial function is another major goal of this application. Position papers on FMD studies 90 state the following: "Typically, significant improvement in FMD can be seen with 20 to 30 patients in a crossover design study and 40 to 60 patients in a parallel-group design study. In studies of this size, the minimal statistically significant improvement that can be detected with intervention is an absolute change in FMD of 1.5% to 2%." The SD of absolute change within subjects in our lab is 0.93%. The sample size proposed (160) will allow us to detect a change of as little as 0.45%. Notably, this change is much more sensitive—approximately one quarter of what is commonly seen with typical sample sizes in conventional FMD studies.

Analysis

The analyses will begin with descriptive statistics. Overall and by-group descriptive statistics will be calculated and examined graphically. Tests for differences in demographics between the early and delayed start groups and characteristics of dropouts will be computed using t-tests, chi square (or Fisher's exact tests if $n < 6$ per cell) to understand if potential differences exist, although such differences are not expected. Comparison of the three UACR strata will be done to assess if there are differences in the populations recruited. Randomization will be within UACR group so that these differences should not bias the trial.

Primary Analysis

To test the hypothesis that early start EPO will worsen the 24-hour DBP assessed by change from baseline to 12 weeks, a mixed model will be used to analyze the results.

We will fit two separate models:

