- model 1: The outcome variable will be 24h ambulatory diastolic BP. The predictors will be indicator variables for group (early or late start), time (baseline and 12 weeks), stratum (UACR: none, high, very high) and all interactions. The random component of the mixed model will include subject and time. Unstructured covariance will be used with estimation of marginal means by maximum likelihood. We expect the interaction between group by time to be significant. The random coefficient analysis does not require baseline systolic BP as a covariate. If the 3-way interaction term (group x time x stratum) is significant, then results will be reported within each stratum. Confirmatory analyses will utilize change from baseline in clinic diastolic BP.
- model 2: The outcome variable will be 24h ambulatory diastolic BP. The predictors will be indicator variables for period within the delayed start group (early or late), time (baseline and 12 weeks from start of period), stratum (UACR: none, high, very high) and

all their interactions. The random component of the mixed model will include subject and time. We expect the interaction between period by time to be significant. If the 3-way interaction term is significant, then results will be reported within each stratum.

Accounting for missing data

Ambulatory BP recording, the gold-standard to assess BP, is carried out only twice during the trial in the parallel group analysis, but clinic BP measurements occur every 4 weeks. Patients who drop out but have some post-baseline measurements of clinic BP will be included in the analyses, thus minimizing loss to follow up. We will impute ambulatory BP as follows: we will use the complete data to build a model that relates the follow-up mean 24-hour ambulatory diastolic BP from the baseline 24-hour ambulatory diastolic BP and the clinic measures using repeated measures Mixed Model regression - then use the expected value from the model for the missing value - and use PROC MI (which generates maybe 5 replicate values to insert variability into the imputation) so that there is a price to pay for imputing.

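### The plan does not say that the overall group-by-time effect stays the primary result when the UACR three-way interaction is significant, nor how strata are weighted

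*Combined protocol and SAP*

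**What the plan says.** For the initial 12-week period, the text on the trial design, below Figure 2, defines the main comparison without any condition: "The primary analysis will compare the 80 participants in the early start group to the 80 in the delayed start (DS) or waitlisted group". The Sample Size section is built on that single contrast: "the required sample size to detect a between-group difference of 5 mmHg is 68 subjects completing the study in each group".

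Under Primary Analysis, model 1 has indicator variables for group, time and "stratum (UACR: none, high, very high) and all interactions". Marginal means are to be estimated by maximum likelihood. The expected finding is stated as "We expect the interaction between group by time to be significant". Then comes the rule at issue: "If the 3-way interaction term (group x time x stratum) is significant, then results will be reported within each stratum". Model 2, which compares the two periods within the delayed-start group, carries an equivalent rule for its own three-way term.

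The plan gives no significance level for the interaction test, no weights for averaging over strata, no multiplicity rule for three stratum results and no expected stratum sizes. It also does not say whether the three-way term stays in the model when it is not significant.

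**The concern.** Two things are left open, and both affect what the trial will report as its answer.

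First, reporting depends on a preliminary test. When the three-way term is significant, two analysts could read the plan differently. One would keep the overall effect as the primary conclusion and add stratum results. The other would let the three stratum results stand as the conclusion. The second reading adds unadjusted chances of a positive finding and rests the answer on subgroups for which the trial was not sized.

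Second, with all interactions in the model, the overall effect has to be built as an average over strata, and its weights decide both what is estimated and how precisely. This matters even when the interaction test is not significant. Equal weights on unequal strata lose precision compared with the contrast used for the sample size.

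**Working it through.** **Inputs.** From Sample Size: a difference of 5 mmHg; for the change in 24-hour diastolic BP, "the standard deviation of the difference was 10.3 mmHg"; "two-tailed tests and 80% power"; 68 completers per arm; 85% completion. From Primary Analysis: three strata. From Method of Randomization: 1:1 allocation within strata.

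**Assumptions.** Alpha is not stated; 0.05 is used because it reproduces the plan's figure. Stratum shares are not stated; equal thirds, 50/30/20 and 60/25/15 are shown. The SD is taken as 10.3 mmHg in every stratum.

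**1. The plan's own figure.** Standard error of the overall difference = 10.3 × √(2/68) = 1.77 mmHg. The two-sample t-test has power 79.7% at 67 per arm and 80.2% at 68, so 68 reproduces. 68/0.85 = 80 per arm, 160 in total.

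**2. Power within a stratum.** Completers per arm in a stratum = 68 × share; two-sample t-test, 5 mmHg, alpha 0.05.

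| Split | Completers per arm | Power |
|---|---|---|
| Equal thirds | 22.7 each | 35.9% each |
| 50/30/20 | 34.0, 20.4, 13.6 | 50.5%, 32.7%, 23.0% |
| 60/25/15 | 40.8, 17.0, 10.2 | 58.2%, 27.9%, 18.0% |

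Counting all 160 randomized (26.7 per arm in each equal stratum) gives 41.3%. With a Bonferroni correction over three equal strata of completers, power is 20.8%. The difference detectable with 80% power in one equal stratum is (1.96 + 0.84) × 10.3 × √(2/22.7), about 8.6 mmHg.

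**3. Error rate if stratum results stand in for the overall result.** Simulated rule: a chi-square test of heterogeneity (2 df, 0.05) across the three stratum differences. If it is not significant, the overall test is used; if it is, any stratum significant at an unadjusted 0.05 counts as positive.

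With no effect in any stratum:
- The heterogeneity test is significant in 5% of trials.
- When it is, at least one stratum is significant in about 85% of trials (equal strata).
- The overall test is positive 5% of the time among the other 95%.
- Total = 0.95 × 0.05 + 0.05 × 0.85 = 0.0475 + 0.0425 = 9.0%.

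A 50/30/20 split also gives about 9%.

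**4. The same rule when there is an effect.** With 5 mmHg in every stratum, the interaction test is significant in 5% of trials. Some positive result appears in about 82% of trials, against 81% for the overall test alone (normal approximation). With true effects of 2, 5 and 8 mmHg in equal strata, the interaction test is significant in 22% of trials; with 0, 5 and 10 mmHg, in 53%.

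**5. Equal weighting of strata.** Variance relative to the unstratified contrast = Σ (1/3)²/share.
- Equal thirds: 1.000, no loss.
- 50/30/20: (1/9) × (2 + 3.333 + 5) = 1.148. Effective 68/1.148 = 59.2 per arm, power 75%.
- 60/25/15: (1/9) × (1.667 + 4 + 6.667) = 1.370. Effective 68/1.370 = 49.6 per arm, power 67%.

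**The case against.** The best defence is that the plan already has an overall primary analysis. The design section defines it without condition, the sample size is computed for it, and the first mediation regression tests the total effect of group on BP change with no stratum terms, so an overall estimate will exist in any case. UACR is the randomization factor, the interaction is a single pre-specified test, and showing stratum effects when they differ is ordinary practice. All of this stands, and it limits the point to one of definition. It does not settle which result is the conclusion when the interaction is significant.

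Three stronger readings are tempting and are not supported:

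- A reader might infer that the overall result is replaced. The sentence says only that results are reported by stratum; it neither withdraws nor retains the overall estimate.
- A reader might infer that the primary test is just the effect in the reference stratum, because indicator variables are used with all interactions. The plan specifies marginal means, which average over strata. What is missing is the weights.
- A reader might infer that the main harm is lost power, with 36% in each stratum. That figure needs equal strata and the same 5 mmHg effect everywhere, whereas the rule operates when effects appear to differ. With a uniform effect it operates in 1 trial in 20, and the chance of some positive result does not fall.

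The completers-only count is also the cautious case, since the plan imputes ambulatory BP for some dropouts.

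**Conclusion.** The point holds as a gap in the definition of the primary result. Model 1 makes reporting depend on a preliminary test and does not say that the overall group-by-time effect remains the conclusion; model 2 does the same for period by time.

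The main cost is error control: about 9% false positives instead of 5%. This applies only if stratum results stand in for the overall one, and it assumes alpha 0.05 and unadjusted stratum tests.

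The second cost is precision. Equal weighting would bring overall power from 80% to about 75% or 67% under the two unequal splits, and would cost nothing if strata are equal. The weights and the shares are both assumptions.

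The low power within strata shows that those results cannot carry the primary conclusion. It is not in itself a loss for the overall test. The trial is not invalidated, but its primary conclusion is not uniquely defined, and this can be settled before analysis.

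**What to change.** State in the Primary Analysis section that the overall group-by-time effect is the primary result whatever the three-way test shows. Estimate it from a model with group, time, group × time, stratum and stratum × time. Alternatively, keep the full model and take the marginal contrast weighted by observed stratum size.

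State the significance level for the primary test. Test the three-way interaction in a separate secondary model, with its threshold given. Report stratum estimates with confidence intervals as supportive.

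Make the same statement for the overall period-by-time effect in model 2.

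The cost is a few sentences of SAP text, with no change to data collection or sample size. The one small downside is that stratum results become supportive only, even if effects truly differ between strata.

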On the other hand, HIF stabilizers may raise EPO to more physiologic levels, reduce crosstalk with vascular EPO-receptors, and mitigate hypertension. A 2014 study demonstrated in a rodent model that compared to EPO, treatment with HIF-stabilizer molidustat corrected anemia associated with subtotal nephrectomy. However, in contrast to EPO, molidustat reduced systolic BP in a dose-dependent manner⁸². The authors postulate that anti-inflammatory and anti-fibrotic effects of the drug on the kidney may be operative. This study further illustrates that increment in Hgb can be dissociated from an increment in BP. Human data are available but are thus far inadequate to address the question of risk for or protection from incident hypertension with HIF stabilizers ⁸³⁻⁸⁶.

RESEARCH PROTOCOL AND TRIAL DESIGN

Overall trial design and plan

To test the notion that EPO treatment in anemic patients with CKD and stage 1 or less hypertension that is treated or untreated with antihypertensive medications will raise BP, we propose a randomized controlled trial with a “waiting-list design” as shown in **Figure 2**. In this design, half of the patients are treated immediately with EPO and the other half are put on a waiting list for 12 weeks, after which they begin treatment. Ultimately, the waitlisted patients are exposed to the intervention, thus serving as their own controls. The design allows between-group comparison by comparing responses in the parallel groups over 12 weeks and within-group comparison for the waitlist group in the second 12 weeks compared to the first 12 weeks. Titration of the dose of EPO will occur every 4 weeks to manage anemia as detailed below. The effect of EPO on BP will be assessed by change in diastolic ambulatory BP measured over 24 hours at baseline and again at 12 weeks in both groups and at 24 weeks in the waitlisted group. At baseline and every 4 weeks thereafter, we will also evaluate changes in clinic BP and albuminuria. At baseline and 4 weeks after intervention, we will measure endothelial function, and collect blood for biomarkers. The biomarkers we will be analyzing are renin, aldo, ET-1, catecholamine, ADMA, and urine nitrates and nitrites.

Figure 2: Trial design and study process

Visit		1	2-3	4	5	6-7	8	9	10
Measurement		Consent	Baseline	Week 4	Week 8	Week 12	Week 16	Week 20	Week 24
PROC	FMD		x	x		DS	DS		
HTN	24h-ABPM		x			x			DS
	Clinic BP	x	x	x	x	x	DS	DS	DS
Labs	24h-urine		x			x			DS
	Blood labs*	x**	x	x	x	x	DS	DS	DS

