Longitudinal resting images will be acquired before inflation. Blood flow estimated by the pulsed Doppler velocity signal using the outer envelope technique to calculate the velocity time integral will be obtained from a mid-artery sample volume at baseline and upon immediate cuff release to assess hyperemic velocity. Peak hyperemic velocity will be determined from the first complete velocity envelope after cuff release. Higher values of hyperemic velocity represent better microvascular dilatation ⁹³. Longitudinal images of the artery in B mode will be continuously recorded for 3 min after cuff deflation. Images will be recorded digitally using an R-wave gated digitizing interface external to the machine (MIA- LLC, Coralville, IA).

A few minutes after deflation, another image will be acquired to reflect a reestablished baseline. The above procedure is repeated to acquire the images in

deviation of 0.93% and between-subject standard deviation of 1.77%. Thus, the test-retest coefficient of variation was 7.2% in our laboratory.

Biomarker measurements

We may use specimen collected as part of this study for analysis of DNA which may include whole genome sequencing. Plasma endothelin-1 will be measured using validated ELISA kits (R&D systems, Inc., Minneapolis, MN). 24h urinary nitrite and nitrate and total nitrates will be measured using the Greiss reaction using kits from R&D systems, Inc. Renin and aldosterone will be measured using a commercial laboratory (LabCorp, Burlington, NC). Plasma ADMA will be measured using LCMS in our biochemistry core lab. The usual labs such as blood counts, chemistries, urine albumin and Na will be measured in the hospital laboratory. Renin + aldosterone lab testing will require the participants to be resting in seated position for at least 15 minutes prior to blood draw.

STATISTICAL METHODS

Outcome Variables

The outcome variables are as follows:

1. Change from baseline to 12 weeks in diastolic BP in EPO treated patients compared to delayed start controls. In the waitlisted group, we will measure the change from 12 weeks to 24 weeks compared to the change from 0 to 12 weeks.

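### Model 2 needs four ambulatory readings per delayed-start patient but only three are scheduled; the use of week 12 is unstated, and entering it twice can misstate the standard error

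*Combined protocol and SAP*

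**What the plan says.** - **Recordings.** Under Overall trial design and plan, diastolic ambulatory BP is "measured over 24 hours at baseline and again at 12 weeks in both groups and at 24 weeks in the waitlisted group". Study Intervention gives the count: ambulatory monitoring, "which will be done twice in the immediate start group and 3 times in the delayed start group". The Figure 2 schedule agrees.
- **Role.** The text after Figure 2 says "Confirmatory analysis will compare the first 12 weeks to the next 12 weeks in the DS group".
- **Comparison intended.** Outcome Variables says that in the waitlisted group "we will measure the change from 12 weeks to 24 weeks compared to the change from 0 to 12 weeks".
- **Model.** Under Primary Analysis, the model 2 predictors are "period within the delayed start group (early or late), time (baseline and 12 weeks from start of period"), UACR stratum in three levels, and all interactions, with subject and time as the random component. It adds "We expect the interaction between period by time to be significant" and "If the 3-way interaction term is significant, then results will be reported within each stratum".

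Unstructured covariance and maximum likelihood are stated for model 1 only. Nothing says how the week-12 recording enters model 2.

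**The concern.** Crossing two periods with two times gives four cells per patient. The week-12 recording is both the end of the early period and the baseline of the late period, and no separate late-period baseline is scheduled. The model as written therefore either lacks a cell or uses one reading as if it were two.

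Two things are at stake: the confidence interval and test for the confirmatory within-group comparison, and the three-way test that decides whether results are reported by stratum.

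**Working it through.** **1. The plan's own figure.** Sample Size states: "The mean difference was 0.14 mmHg and the standard deviation of the difference was 10.3 mmHg". For 5 mmHg and 80% power, 2 × (1.96 + 0.8416)² × 10.3² / 5² = 66.6, so 67 per group by the normal approximation and 68 with the t distribution. Then 68/0.85 = 80. The stated figures reproduce. They size model 1; no standard error or power is given for model 2.

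**2. Can the interaction be estimated?** The columns are intercept, period, time and period × time.
- Week 12 entered once, under either label: three cells filled, rank 3 of 4. With three strata, rank 9 of 12.
- Week 12 entered twice: rank 4 of 4, and 12 of 12 with strata.

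**3. Point estimate with week 12 twice.** On rows (Y0, Y12, Y12, Y24) the interaction is (Y24 − Y12) − (Y12 − Y0) = Y24 − 2·Y12 + Y0, which is the comparison in Outcome Variables. Duplication does not change the estimate.

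**4. Standard error.** Let D be the SD of each 12-week change, c the correlation between the two changes, and n the number of completers.
- True variance: 2D²(1 − c)/n.
- Variance reported by a random-intercept fit on the four rows: residual variance D²(3 + c)/6, times 4/n, which is 2D²(3 + c)/(3n).
- Ratio, reported to true: (3 + c)/[3(1 − c)].

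Inputs: D = 10.3 and n = 68 from Sample Size. Assumptions: two-sided alpha 0.05, and the 4-week SD applying to both 12-week changes, untreated and treated. The documents do not give c, so a range is shown. With 2D²/n = 2 × 106.09/68 = 3.12:

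| c | True SE | Reported SE | Ratio of SEs | Type I error | Three-way test (2 df) |
|---|---|---|---|---|---|
| −0.5 | 2.16 | 1.61 | 0.745 | 14.4% | 18.9% |
| −0.25 | 1.97 | 1.69 | 0.856 | 9.3% | 11.1% |
| 0 | 1.77 | 1.77 | 1.000 | 5.0% | 5.0% |
| +0.2 | 1.58 | 1.82 | 1.155 | 2.4% | 1.8% |

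Type I error is 2 × [1 − Φ(1.96 × SE ratio)]. For the three-way test it is exp(−(5.99/2) × variance ratio). Null simulation of the random-intercept fit (100,000 replicates; assumed strata of 23/23/22 and between-patient SD of 8 mmHg) gave 14.5, 9.2, 5.0 and 2.4%, and 18.8, 11.2, 5.1 and 2.0% for the three-way test.

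**5. Adding random time.** Without a lower bound, the fitted time variance would be D²c/2, or −26.5 at c = −0.5. A valid fit holds it at zero when c is negative, so the random-intercept result returns. Simulated type I error by maximum likelihood was about 15% at c = −0.5 and 10–11% at −0.25. At c = 0 it was 6.6% and at +0.2 it was 3.5% (5,000 replicates).

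**6. Unstructured residual covariance on four rows.** Two of the four columns are identical, so the matrix is singular.

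**7. Which sign of c is likely?** The two changes share Y12 with opposite sign. With exchangeable visits, c = −0.5. With visit-noise SD s and patient-specific linear drift of SD t per 12 weeks, c = (t² − s²)/(t² + 2s²), which reaches 0 only when t = s. If 10.3 is the 12-week SD, 3s² = 10.3² puts that point at 5.9 mmHg.

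**The case against.** **The direction is not known.** This stands. A reader might infer that the confirmatory test runs at 14%. The documents do not support that: 14% is the exchangeable case, the largest shown, and with positive c the test is conservative. Negative c is the more plausible direction, but it is an expectation and not a figure from the plan.

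**The random time term, or unstructured covariance, might absorb the problem.** Neither does. Random time would moderate the error at negative c only through a negative variance. Carrying model 1's unstructured covariance over to four residual rows gives a singular matrix. On that reading the analysis fails visibly instead of giving a silently narrow interval, and it is still not a usable specification.

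**Week 12 spans two visits, so there might be two recordings.** Study Intervention explains that one 24-hour recording needs two consecutive days, and it counts three recordings in all.

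**Model 2 is supportive.** This largely stands. The between-group comparison is primary, the sample size rests on it, and no alpha is allocated to model 2. But the plan calls the within-group comparison confirmatory and lists model 2 under Primary Analysis.

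**The analyst would notice and repair it.** Probably, but the choice would then be made after the data are in hand.

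**Conclusion.** The point holds. As written, model 2 either cannot estimate its test term or runs on a duplicated reading. In the second case its standard error is correct only in special circumstances: at c = 0 for the random-intercept fit, and not quite there for maximum likelihood with random time. Over c from −0.5 to +0.2, the random-intercept fit has type I error from about 14% down to about 2.4%, and the three-way stratum test from about 19% down to about 2%. These sizes rest on the assumptions in step 4 of the working, chiefly the transfer of a 4-week SD to both 12-week periods.

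A reader might go further and infer that the within-group estimate is biased by the duplication, or that the trial's main result is in doubt. Neither follows. The estimate is the intended contrast, and model 1, the randomized comparison and the sample size are untouched. Regression to the mean after selection on baseline BP is a separate matter and no part of this point. The wording should be fixed before analysis.

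**What to change.** Replace the model 2 specification with wording such as:

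> Each delayed-start 24-h ABPM is entered once (weeks 0, 12, 24). Fixed effects are visit (3 levels), stratum and stratum × visit, with unstructured within-patient covariance, fitted by REML with Kenward-Roger degrees of freedom (or, in patients with all three readings, a t-test of the per-patient contrast). The within-group test is the contrast +1, −2, +1 on weeks 0, 12, 24, averaged over strata. The three-way test asks whether this contrast differs between strata.

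This keeps the sponsor's comparison. Its validity does not depend on c: in simulation the three-visit contrast rejected in 4.9–5.0% of null replicates at every c shown. The estimator has to be named. With maximum likelihood and three strata, the variance shrinks by 65/68, and type I error is about 6.0% with a normal reference or 5.5% with t on 65 degrees of freedom.

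**Cost.** SAP wording only; no new visit or measurement. Against the random-intercept fit, the confidence interval widens by about 34% at c = −0.5 (2.16/1.61) and 17% at c = −0.25 (1.97/1.69). It is essentially unchanged at c = 0 and narrows by about 13% at c = +0.2 (1.58/1.82). At c = −0.5, the correct standard error gives about 64% power for a 5 mmHg contrast with 68 completers: Φ(5/2.16 − 1.96).
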